1	Theme: Wake up from automatic pilot Activities: relationship building; orientation; establishment of ground rules; eating practice; 10- min body scan (thought, sensations and feelings); enquiry	Theme: Orientation Activities: relationship building; orientation; establishment of ground rules; program introduction; service information; enquiry
2	Theme Knowing in the awareness Activities: Doing mind exercise (thoughts are not facts); 10- min body scan; 10- min sitting meditation; enquiry	Theme: Understanding psychosis I Activities: introduction; conceptualizations of psychosis; biopsychosocial factors in psychosis; enquiry
3	Theme: Living to the present Activities: pleasant experiences calendar; stretch and breath meditation; 10- min sitting with breath and body; enquiry	Theme: Understanding psychosis II Activities: the stress-vulnerability model; symptoms of psychosis; the phases model; enquiry
4	Theme: Gathering the wandering mind Activities: unpleasant experiences calendar; mindful stretching; 3-minute breathing space; enquiry	Theme: Understanding psychosis III Activities: understanding diagnosis; common myths about psychosis; co-occurring psychiatric conditions; enquiry
5	Theme: Looking out the aversion Activities: freeze-framing aversion; defining the territory of psychosis; 3-min breathing space; enquiry	Theme: Understanding psychosis IV Activities: psychosis in the acute, early, late and incomplete recovery; enquiry
6	Theme: Attending the experience but not thoughts Activities: 15- min sitting meditation with choice awareness; mindful walking; 3-min breathing space, enquiry	Theme: Understanding treatment I Activities: introduction; psychosocial interventions; enquiry
7	Theme: Allowing Activities: 15- min sitting meditation with difficulties (negative self schema); 3-min breathing space (response); enquiry	Theme: Understanding treatment II Activities: medical treatment; aims and benefits of a medication and its potential side effects; enquiry
8	Theme: Thoughts are not facts Activities: 10- min sitting with breaths, body, sounds and thoughts/feelings; alternative viewpoints exercise (positive self schema); 3-min breathing space	Theme: Medication adherence Activities: medication regimen and its benefits

	(response to thought); enquiry	
9	Theme: Responding thoughts Activities: early warning activity; 3-minute breathing space; my relapse signature activity; enquiry	Theme: Discontinuing medication Activities: pros and cons; risk of relapse; side-effects; physical health; enquiry
10	Theme: Kindness the healing Activities: mastery and pleasure activity; nourishing and depleting; 3-minute breathing space (regular and responsive); enquiry	Theme: Involuntary treatment Activities: information about and reason for involuntary treatment; legal rights; enquiry
11	Theme: Making a difference Activities: an action plan; 3- minute breathing space (regular); enquiry	Theme: Relapse prevention Activities: introduction; relapse prevention; early warning signs; enquiry
12	Theme: Practice momentum and ending Activities: 10- min body scan; review; personal reflections; plans for practice continuum; closing sitting	Theme: Developing a wellbeing plan Activities: sleep hygiene; managing stress; reducing substance use; keeping healthy; enquiry

[figure not shown]
Appendix 2 Guidelines to Semi-structured Focus Group Interview

The interview may follow the questions as below:

We are interested in finding out about your experiences of the mindfulness program

Interview Questions	
1	What did you expect from the mindfulness program when you started?
2	Did the program reflect what you expected? How so? How not so?
3	How would you describe what the program is about and what you have learned?
4	What keeps you coming back to and finish the mindfulness program?
5	What do you particularly like about the mindfulness program?
6	What do you dislike or like less about the mindfulness program?
7	What is the most difficult and/or easy mindfulness activity?
8	What is it like using mindfulness? How would you describe mindfulness for you?
9	What have you found helpful or not so helpful about the mindfulness program?
10	How have you been feeling emotionally/physically/socially since the mindfulness program began? Any differences between now and before you joint the program?
11	What difficulties have you experienced in doing the homework?
12	Have you ever experienced any psychotic symptom? If yes, how did you respond to it?
13	In what way do you think that you have benefited from practicing mindfulness?
14	Did you find learning mindfulness in a group to be helpful?
15	What form might the mindfulness practice take place in the future?
16	How do you think people with psychosis should be best supported in community services?
17	What do you think could be done to improve the treatment program? Time, place, duration?
18	Is there anything you would like to mention and we have not covered in our discussion today?

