Five Facet Mindfulness Questionnaire (FFMQ) (Baer et al, 2006) is a 39-item self-report questionnaire that measures five facets of mindfulness: observing; describing; acting with awareness; non-judging and non-reacting. The internal consistency for each of the five facets are $\alpha=0.83$, $\alpha=0.91$, $\alpha=0.87$, $\alpha=0.87$ and $\alpha=0.75$ accordingly. Items are scored on a 5-point Likert scale ranging from 1 (never or very rarely true) to 5 (very often or always true). The Chinese version of the Five Facet Mindfulness Questionnaire (FFMQ-C) obtained a good test-retest reliability (0.88) and a high internal consistency (0.83 in the community sample and 0.80 in the clinical sample) (Hou, Wong, Lo and Mak, 2013). A short form scale of the FFMQ (FFMQ-SF) is highly and significantly correlated with the FFMQ-C ($r=0.96$), and explained 91.3% of the variance of the FFMQ-C which will be adapted for the purposes of the study.

The last outcome assessment will be the number and length of re-hospitalization referenced from the case files and self-reporting.

Regarding the qualitative data obtained by focus group interviews, it will be used to determine the common themes being mentioned most frequently by participants and organized under different categories such as expectations, positive and negative outcomes, personal difficulties, positive and negative comments about the program and description.

Data collection procedure

There will be two research assistants (RA), RA1 will be responsible for conducting the psychoeducation program and RA2 will be blinded and doing data collection. The RA2 will conduct the baseline measurements after obtaining the written consent and following comprehensive explanations about the study purpose and procedure and its ethical issues. After that, the participants will be assigned randomly to either study group or control group. Patients' outcomes at the ICCMWs will be measured at one week post-intervention using the same set of questionnaires as the baseline measures.

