Two groups of 3-4 participants in treatment group will be interviewed in a quiet interview room in the ICCMWs, or as preferred by the participants. Participants with significant positive changes, minimal changes and negative changes will be invited according to the baseline and Post-test 1 measurement. Interviews in a focus group format will be conducted to identify the strengths and limitations and therapeutic components from the participants' perspective. Interview questions will be developed based on an open and broad basis criterion (Appendix 2). Audio-recorded group sessions will also be used to examine the group process/dynamics and participants' involvement and appraisals of the group program.

The outcome measurements will be completed by the participants at three and six months after the interventions with the help of RA1 who will be blind to the participants' assigned groups. By self-reporting or case files reviewing, re-hospitalizations of the participants will also be examined and calculated and checked against their medical records. Participants' recruitment, interventions, data (outcomes) collection, and data analyses are outlined in a flow diagram of Appendix 3, as recommended by the latest CONSORT statement.

Data Analysis

Intention-to-treat (ITT) analyses (Fisher et al, 1989) will be used to provide a more conservative estimate of outcomes. By using IBM SPSS, version 23.0, all data on participants' socio-demographic illness-related characteristics, attendance and completion rate, and study outcomes will be numerically coded, summarized and analyzed. Repeated-measures ANOVA tests will be used to assess any significant differences on all dependent (outcome) variables within and between groups and across three post-tests (one week, 3 months and 6 months follow-up).

Sub-group analysis for participants who will complete all sessions and those completers, and the outliers which can have deleterious effects on statistical analyses will also be screened. Defined completers will be those who have attended at least eight sessions by which the main themes of the program are covered (Nose, Barbui and Tansella, 2003).

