Mediation analyses will be conducted to examine covariates of change in emotions and distress associated with psychotic symptoms by multiple regression analysis. Within – subjects effect sizes will also be reported based on Cohen's d statistic. Kaplan Meier survival analysis will be used for the analysis of re-hospitalization rates across treatment and control groups. The significance level of all statistical tests will be set at 5%. Clinical significance will be all subscales of DASS-21 shows a percentage improvement in mean scores in the range of approximately 45–55% pre- and post-intervention (Ng, Trauer, Dodd, Callaly, Campbell and Berk, 2007). For example, the mean DASS severity ratings of depression in pre-intervention is 31.2 and 16.2 in a week post-intervention. The difference is 15.0 and the percent change is 48.1 which is clinical significant. Reliable Change Index (RCI) will take into account the reliability of assessment instrument on scores of each participant between the pre-test and one post-test divided by the standard error of the difference between the two scores. Any value of RCI >1.96 (at p<0.05) will be considered statistically significant (Jacobson & Truax, 1991).

NVivo will be used to analyze the qualitative data on subjective experiences to mindfulness and acceptability to the interventions (Krippendorff, 2004). All audio-taped interviews will be transcribed into Cantonese/Chinese by the research assistant and checked for accuracy of transcription by the researcher. The revised transcripts

will be coded independently and important manifest and meanings in the data will be identified.

Ethical considerations

Approval for human subject research will be obtained from the three ICCMWs and Edinburgh Napier University before the start of data collection. The researcher will ensure and inform the potential participants that participation in the study is voluntary and that withdrawal from the study at any time will not affect any aspects of care. The information leaflet and consent form will be developed according to the format recommended by School of Health and Social Care ethics committee. All participants will be assured of the confidentiality of the data provided and the anonymity of their personal identity, and asked for permission to tape record the interviews and intervention sessions if selected. All data will be safely kept in a locked cabinet accessible only by the researcher.

Adverse events reporting and monitoring

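### MBCTp participants lost before Post-test 1 cannot be invited to the focus groups, two guide items presuppose finishing and benefit, and the acceptability claim is wider than the group interviewed

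*SAP*

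**What the plan says.** **Who is interviewed** (SAP, Data collection procedure). "Two groups of 3-4 participants in treatment group will be interviewed", which makes 6 to 8 people, all from the MBCTp arm. The selection rule is: "Participants with significant positive changes, minimal changes and negative changes will be invited according to the baseline and Post-test 1 measurement". The same section fixes the first follow-up: "Patients' outcomes at the ICCMWs will be measured at one week post-intervention". Data Analysis lists three post-tests, the first at one week, so Post-test 1 is that assessment.

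**How they are asked.** The same section sets a standard for the guide: "Interview questions will be developed based on an open and broad basis criterion". Of the 18 items in Appendix 2, item 4 asks "What keeps you coming back to and finish the mindfulness program", item 12 begins "Have you ever experienced any psychotic symptom", and item 13 asks "In what way do you think that you have benefited from practicing mindfulness".

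**What the answers are for** (Data Analysis). The qualitative data concern "subjective experiences to mindfulness and acceptability to the interventions".

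**What is recorded elsewhere.** Interventions has attendance and dropout monitored in both arms. Data Analysis defines a completer as someone who attended at least eight sessions. Sample size allows for 15% attrition, giving 48 per group.

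**The concern.** Reasons for leaving a programme are central evidence on whether it is acceptable. The invitation rule cannot reach people who left the study before Post-test 1, and it ignores attendance for everyone else. A log that could identify people who stopped coming is kept but plays no part in the invitation.

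Two items add to this. Item 4 can be answered as worded only by someone who came back and finished. Item 13 takes benefit for granted and asks only about its form. Both fall short of the openness the plan sets for itself.

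The acceptability wording also covers more than the data can support: with no PEp participant interviewed and a guide about the mindfulness programme, nothing can be said about how acceptable PEp was.

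At stake is the qualitative statement on acceptability, which could come out more favourable to MBCTp than the experience of the whole arm warrants.

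**Working it through.** **1. The plan's own attrition figure.** Inputs from Sample size: 82 participants, 41 per group, 15% attrition. 82 × 1.15 = 94.3, rounded up to 95; 41 × 1.15 = 47.15, rounded up to 48 per group. Both stated figures are reproduced.

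**2. People at risk of exclusion.** 48 × 0.15 = 7.2, taken as 7 in the MBCTp arm. The plan does not say when the 15% is lost. Treating all 7 as lost before Post-test 1 is an assumption and an upper case within the planned attrition; 4 lost by then serves as a lower illustration.

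**3. Chance of invitation under the rule.** The three invitation classes are positive, minimal and negative change from baseline to Post-test 1. Without Post-test 1 there is no change score and so no class. No other route is given, so the chance is 0.

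**4. Yardstick.** For a simple random draw of n from 48, of whom m were lost, P(at least one) = 1 − C(48 − m, n) / C(48, n), and the expected number is n × m / 48.

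| m lost before Post-test 1 | n = 6 | n = 8 |
|---|---|---|
| 7 | 1 − C(41,6)/C(48,6) = 0.634 | 1 − C(41,8)/C(48,8) = 0.747 |
| 4 | 1 − C(44,6)/C(48,6) = 0.425 | 1 − C(44,8)/C(48,8) = 0.530 |

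With m = 7 the expected number is 6 × 7/48 = 0.9 to 8 × 7/48 = 1.2. The plan samples purposively, so the random draw only gives scale. It also assumes that the people lost could be reached and would agree.

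**5. The guide, item by item.** Items 4 and 13 carry a presupposition. Against them, item 2 asks how the programme failed to match expectations, 6 asks about dislikes, 7 about the most difficult activity, 9 about what was less helpful, 10 about how participants have felt and what has changed (in either direction), 11 about homework difficulties, 17 about improvements, and 18 about anything not covered. So 2 of 18 items are leading, and eight leave room for a negative account.

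**6. Claim against source.** Data Analysis refers to interventions in the plural; Data collection procedure restricts interviews to the treatment group. The two do not match unless the plural is read as MBCTp only.

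**The case against.** The strongest reply is that the plan already looks for negative accounts. It deliberately invites people with minimal and negative change. Its coding categories (Outcome Evaluation) include negative outcomes, personal difficulties and negative comments. The guide is semi-structured and may, rather than must, be followed. Recorded sessions are also used to study involvement and appraisals, and could capture people who later left. Attendance and completion rates are analysed, so leaving is itself recorded. All of this stands, and it limits the point. It does not give people without Post-test 1 a way to be interviewed, and none of these sources asks them why they left.

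Some stronger readings are tempting and should be set aside:

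- A reader might infer that nobody who left the sessions can be heard. The documents do not support this: invitations are not limited to completers, and someone who stopped attending but was still assessed at one week can be invited.
- A reader might infer that the guide as a whole assumes success. It does not; see the item count above.
- A reader might take item 12 as a failure to detect harm from practice. Its opening is uninformative in people admitted with a psychotic diagnosis, but it goes on to ask how the participant responded. Adverse events, including disturbing psychotic symptoms, are recorded and reviewed separately under Adverse events reporting and monitoring.

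On the plural, it can fairly be said that Interventions uses the term intervention groups for the MBCTp groups. That makes the mismatch a matter of clarification, but the wording still invites a conclusion about PEp.

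**Conclusion.** The point holds in a limited form. MBCTp participants lost before Post-test 1 cannot be selected, no place is reserved for people who stopped attending, items 4 and 13 are leading, and the acceptability statement is broader than the people interviewed.

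It would go too far to call the acceptability result biased: the direction of any tilt is plausible but not demonstrated. The size depends on when attrition occurs and on whether those lost would take part, and the plan gives neither. The 63% to 75% figure is therefore an upper illustration within the planned attrition, and 42% to 53% applies if 4 are lost. The certain part is the zero chance under the rule.

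The matter is confined to the qualitative strand. The DASS-21 comparison and adverse-event reporting are untouched. The change is worth making because it is cheap and must come before the interviews.

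**What to change.** - **Invitation.** Within the same 6 to 8 places, add a category for participants who attended fewer than eight sessions, taken from the attendance records, whether or not they gave Post-test 1.
- **Item 4.** Reword to: *What made you continue with, or stop, the program?*
- **Item 13.** Reword to: *In what ways, if any, has practicing mindfulness helped you or made things worse?*
- **Item 12 (optional).** Tie it to the programme period, keep it open, and keep its follow-up on how the participant responded. A closed prompt towards harm would break the plan's own standard of openness.
- **Data Analysis.** Restrict the acceptability phrase to *acceptability of MBCTp among those interviewed*.

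Cost: one or two fewer places for people who stayed, and some who left may decline. If they do, the number approached and the number who declined should be reported with the findings.
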